**For Patients with Non-Measurable Disease (i.e., Non-Target Disease)**

| Non-Target Lesions | New Lesions | Overall Response |
|--------------------|-------------|------------------|
| CR                 | No          | CR               |
| Non-CR/non-PD      | No          | Non-CR/non-PD*   |
| Not all evaluated  | No          | not evaluated    |
| Unequivocal PD     | Yes or No   | PD               |
| Any                | Yes         | PD               |

\*‘Non-CR/non-PD’ is preferred over ‘stable disease’ for non-target disease since SD is increasingly used as an endpoint for assessment of efficacy in some trials so to assign this category when no lesions can be measured is not advised

## **10. DATA REPORTING / REGULATORY REQUIREMENTS**

### **10.1 Data Reporting**

#### **10.1.1 Method**

This study will require data submission and reporting via the OnCore Database, which is the official database of the MCC CRO. Instructions for submitting data is listed in Study-Specific Data Management Plans (DMP) created by the CRO staff.

#### **10.1.2 Responsibility for Data Submission**

Study staff are responsible for submitting study data and/or data forms to OnCore as per the MCC CRO's SOPs. This trial will be monitored by the MCC DSMC on a schedule determined by PRMC at its initial review. The CRO staff are responsible for compiling and submitting data for all participants and for providing the data to the PI for review.

## **11. STATISTICAL CONSIDERATIONS AND DATA MANAGEMENT**

### **11.1 Study Design and Sample Size**

A single arm Phase II trial will be performed using FDA approved single agent dosage for both nivolumab and rucaparib. We will estimate the proportion of patients who exhibit PFS at 6 months. Based on a phase III randomized clinical trial conducted by ECOG, the historical median PFS for Stage IV SCLC, post platinum doublet in platinum sensitive patients, is 2.3 months in the observation arm vs 3.6 month on maintenance topotecan arm [23]. Assuming that the proportion who exhibit PFS at 6 months is 50%, a sample of 36 patients produces a one-sided 90% confidence interval with a lower limit equal to 38%, providing some evidence of efficacy.

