Based on preclinical data supporting the role of immune checkpoint inhibitors and PARP inhibitors in small cell lung cancer, we feel that combining these two agents has the potential to prolong progression free survival and overall survival. These two classes of drugs have non-overlapping toxicities. This novel combination has not been tried in a front-line maintenance setting for SCLC.

A single arm Phase II trial will be performed using FDA approved single agent dosage for both nivolumab and rucaparib. Median progression-free survival (PFS) will be compared to historical PFS for stage IV SCLC. Based on a phase III randomized clinical trial conducted by Eastern Oncology Cooperative Group (ECOG), the historical median PFS for Stage IV SCLC post platinum doublet in platinum sensitive patients is 2.3 months in the observation arm vs 3.6 month on maintenance topotecan arm, a 56 % improvement [23]. We expect our experimental combination will outperform topotecan. Assuming a median PFS of 3.6 months from the topotecan arm as historical data, we will hypothesize a 75% improvement with the combination of rucaparib and nivolumab (median PFS = 6.3 months). This is justified by the recently presented data on single agent nivolumab (unpublished) which exhibited exceptional durable responses in second and third line SCLC. Of 59 treated patients with nivolumab 3 mg/kg investigator-assessed objective response rates were 12% (95% CI, 5% to 23%). Responses were observed regardless of tumor-programmed death-ligand 1 status. With a median follow-up of 28 months, 12-month progression-free survival rates were 8%, 12-month OS rates were 39% respectively [49]

Thus, it is reasonable to hypothesize that the proposed combination of nivolumab and rucaparib as maintenance after front line chemotherapy will show even better responses.

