### **11.2 Data Analysis**

#### **Analysis of Primary and Secondary Endpoints**

Progression-free survival will be estimated using the Kaplan-Meier curve and the proportion who do not exhibit PFS at 6 months and at other specific timepoints will be calculated along with confidence intervals. The median PFS and confidence interval will also be calculated. Other time to event endpoints including OS will be estimated using the same methods. The disease control rate, objective response rate and best overall response rate will be estimated, along with exact 95% binomial confidence intervals.

Immune markers including percentage of CD4 T cells and CD8 T cells expressing PD-1 and Ki-67, expression of CD101 and CD38 will be summarized descriptively at baseline and at each time point of evaluation. The change from baseline will also be calculated and compared using paired test statistics. QOL measures will also be summarized using descriptive statistics.

Analysis of baseline whole exome sequencing data (where available) will be performed in the Biostatistics and Bioinformatics Shared Resource at MCC. Customized data processing and data

analysis pipelines will be applied and exploratory comparisons of mutation data with response and clinical outcomes will be performed using Fisher's exact test with control for false discovery rate (FDR).

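### Does the 6-month PFS analysis lack a historical comparator and a defined confidence interval?

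*Combined protocol and SAP*

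**What the plan says.** Section 2.2.5 sets the historical frame. It states "Median progression-free survival (PFS) will be compared to historical PFS for stage IV SCLC" and then fixes the value: "Assuming a median PFS of 3.6 months from the topotecan arm as historical data". It hypothesises a 75% improvement, to a median of 6.3 months.

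Section 11.1 works on a different scale: "We will estimate the proportion of patients who exhibit PFS at 6 months". It repeats that the historical median "is 2.3 months in the observation arm vs 3.6 month on maintenance topotecan arm", assumes 50% progression-free at 6 months, and concludes that "a sample of 36 patients produces a one-sided 90% confidence interval with a lower limit equal to 38%, providing some evidence of efficacy".

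Section 11.2 plans a Kaplan-Meier curve, from which the proportion "at 6 months and at other specific timepoints will be calculated along with confidence intervals". It adds: "The median PFS and confidence interval will also be calculated". The only level attached to an interval in Section 11.2 is for disease control and the response rates, which are reported "along with exact 95% binomial confidence intervals".

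**The concern.** A single-arm result speaks to efficacy only when it is set against an outside value. Here the value in the rationale is a median in months, while the design figure is a proportion at 6 months. The two cannot be compared without a conversion, and Section 11 gives none. Section 11.1 also lists both historical arms without repeating which one is the reference, and the comparison announced in Section 2.2.5 does not reappear in Section 11. The analysis section then leaves the level, sidedness and method of the PFS interval unstated.

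Read strictly, this would let someone choose the interval after seeing the data so that its lower limit falls on the preferred side of a historical rate. For the primary objective of the trial that would be a real weakness, so the size of the freedom has to be worked out.

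**Working it through.** **Inputs.** From Section 11.1: n = 36, assumed 6-month PFS 50% (18/36), one-sided 90% limit stated as 38%. From Section 2.2.5: historical median 3.6 months, target median 6.3 months. Not in the documents: the shape of the historical PFS curve. I assume an exponential curve and show a range.

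**Step 1. The plan's own figure.** The exact (Clopper-Pearson) one-sided 90% lower limit for 18/36 is the 10th percentile of a Beta(18, 19) distribution, 0.3818. This rounds to the stated 38%.

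**Step 2. The reference on the 6-month scale.** For an exponential curve with median m, S(6) = 0.5^(6/m).

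- m = 3.6: 0.5^(6/3.6) = 31.5%
- m = 6.3: 0.5^(6/6.3) = 51.7%

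The 6.3-month target in Section 2.2.5 and the 50% in Section 11.1 therefore agree closely. The change of scale between the two sections does not bring in a different hypothesis.

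**Step 3. The planned result against the reference.** At 18/36 the one-sided 90% limit is 38.2% (exact), 38.9% (log-log) or 40.4% (log-transformed). All exceed 31.5%. With a Weibull curve of median 3.6 months, S(6) = 0.5^((6/3.6)^k). Shapes k = 0.8, 1.2 and 1.5 give 35.2%, 27.8% and 22.5%, and 38% lies above all of them.

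**Step 4. How much the unstated level and method matter.** Lower limits for each count out of 36, with no censoring, to be compared with 31.5%:

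| Progression-free at 6 months | One-sided 90%: exact / log-log / log | Two-sided 95%: exact / log-log / log |
|---|---|---|
| 15 | 30.4 / 31.1 / 32.4% | 25.5 / 25.6 / 28.3% |
| 16 | 32.9 / 33.7 / 35.0% | 27.9 / 28.0 / 30.9% |
| 17 | 35.5 / 36.3 / 37.7% | 30.4 / 30.5 / 33.4% |
| 18 | 38.2 / 38.9 / 40.4% | 32.9 / 32.9 / 36.1% |

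With the one-sided 90% level the limit first exceeds 31.5% at 15/36 (log-transformed) or 16/36 (exact, log-log). With a two-sided 95% interval it does so at 17/36 (log-transformed) or 18/36 (exact, log-log). At 14 or fewer no choice in the table clears the reference, and at 18 or more every choice does.

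**Step 5. Probability of the band in between.** With X binomial(36, 0.5), P(X ≥ 15) − P(X ≥ 18) = 0.879 − 0.566 = 0.312. If the analyst keeps to the one-sided 90% level of Section 11.1, the only count that depends on the method is 15/36, with probability 0.879 − 0.797 = 0.081.

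**The case for a change.** The strongest opposing case is that 31% is not negligible, that the remedy is a few words, and that the sponsor's own choices could be carried straight into Section 11.2. Stating the reference would also show what 36 patients deliver. Requiring at least 16/36 against 31.5% has type I error of about 7% and power of about 80% at a true 50%, and the protocol states neither. All of this is correct as arithmetic, and a sentence joining the three places would make the plan tidier.

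Three things limit it. First, the charge that there is no level and no comparator is too broad. Section 11.1 names the one-sided 90% level for exactly this proportion, and Section 2.2.5 chooses 3.6 months. Listing the 2.3-month observation arm again as background does not reopen that choice.

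Second, the 31% describes how often a limit would move across a line that the plan does not draw. Section 11.1 sets out to estimate and claims only some evidence. Defining success as a limit above 31.5% would add a decision rule to an estimation design, and the line would rest on an assumed curve. Statisticians would differ on whether that is an improvement.

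Third, a heavier-tailed historical curve could put the reference above the planned limit. A Weibull shape of 0.6 gives 39.0%, against 38.2% exact. The documents give no curve shape. Section 2.1 says that most relapses come 3 to 6 months after chemotherapy ends, whereas shape 0.6 places only about 15% of progressions in months 3 to 6, compared with about 25% for the exponential. The text gives no support for that tail.

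**Conclusion.** The observation is accurate as a matter of drafting: Section 11 does not express the 3.6-month reference as a 6-month rate, and Section 11.2 does not repeat the level or name an interval method for PFS. No change follows. No stated figure is wrong, and the 38% reproduces exactly. The reference and the level can both be read from the protocol. Kaplan-Meier estimates of 6-month and median PFS with any standard interval are sound, and the median with its interval can be set beside 3.6 months to meet the comparison announced in Section 2.2.5.

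The open choice touches 15 to 17 out of 36 (31% probability at a true 50%), or 15/36 alone (8%) if the level in Section 11.1 is kept. Even there it alters how a limit compares with an assumed reference, and leaves the reported estimate as it is. These figures assume an exponential historical curve and no censoring before 6 months.

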### **11.2 Data Analysis**

#### **Analysis of Primary and Secondary Endpoints**

Progression-free survival will be estimated using the Kaplan-Meier curve and the proportion who do not exhibit PFS at 6 months and at other specific timepoints will be calculated along with confidence intervals. The median PFS and confidence interval will also be calculated. Other time to event endpoints including OS will be estimated using the same methods. The disease control rate, objective response rate and best overall response rate will be estimated, along with exact 95% binomial confidence intervals.

Immune markers including percentage of CD4 T cells and CD8 T cells expressing PD-1 and Ki-67, expression of CD101 and CD38 will be summarized descriptively at baseline and at each time point of evaluation. The change from baseline will also be calculated and compared using paired test statistics. QOL measures will also be summarized using descriptive statistics.

Analysis of baseline whole exome sequencing data (where available) will be performed in the Biostatistics and Bioinformatics Shared Resource at MCC. Customized data processing and data

analysis pipelines will be applied and exploratory comparisons of mutation data with response and clinical outcomes will be performed using Fisher's exact test with control for false discovery rate (FDR).

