### 1.2 Secondary Objectives:

1.2.1 To evaluate the disease control rate after 8 weeks, 16 weeks and 24 weeks of treatment. Disease control rate is defined as the percentage of subjects who had a partial response post initial chemotherapy and who have a confirmed reduction in tumor size compared to post induction chemotherapy baseline (complete response, CR; partial response, PR) or fulfilling the criteria for stable disease (SD) according to Response Evaluation Criteria in Solid Tumors (RECIST V1.1). Patients with CR will be considered to have disease control if they continue to remain in CR since they do not have measurable disease at baseline.

1.2.2 To evaluate 1-year and 2-year overall survival. Overall survival is defined as the time from first dose of trial medication to date of death due to any cause.

1.2.3 To evaluate potential biomarkers for durability of response, especially tumor mutation burden (refer to Biomarker Section).

1.2.4 To assess the toxicity profile of experimental drug combination.

1.2.5 To evaluate objective response rate at 8 weeks, 16 weeks and 24 weeks. Objective response rate is the proportion of patients with complete response or partial response according to RECIST V1.1. Patients with CR at baseline will be excluded from objective response rate (ORR) analysis.

1.2.6 To evaluate quality of life (QOL). Quality of life is assessed by the validated, standardized EORTC questionnaires (specifically the QLQ-C30 and the LC-13) on screening/pre-study (for pre-treatment baseline), once during treatment, and at the end of treatment. These EORTC QOL measures are located in Appendix D.

1.2.7 To explore in a preliminary manner the response of genomic subsets to treatment focusing on tumor mutation burden, cMEK and TP53 mutation analysis of tumor tissue and evaluation of response, using the Oncology Research Information Exchange Network (ORIEN) consortium whole exome sequencing platform to evaluate tumor mutation burden, somatic and germline mutations.

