#### Analytical procedures

Patient PBMCs will be analyzed by the FCCS SRF for the percentage of cells expressing each marker and for the mean fluorescence intensity for each marker. PBMC samples will be analyzed on a Beckman-Coulter CytoFLEX LX cell analyzer with 19 color detection capacity. Flow cytometric data sets will be interpreted by the MCC Biostatistics and Bioinformatics Shared Resource Facility by computational flow cytometry using SPADE algorithm to automatically identify populations.

12.1.4 Assessment of baseline tumor mutational burden and correlation with radiological response.

All patients enrolled in the study will be assessed as to whether they have also enrolled on the Markey Cancer Center Total Cancer Care (ORIEN protocol; Yes/No status will be documented in the eCRF).

- Patients enrolled on ORIEN protocol undergo whole exome sequencing of tumor tissue (at baseline, and progression, when available) and germline mutation testing via peripheral blood or buccal swab. Genomic profiling will be done under Markey Cancer Center Total Cancer Care (ORIEN) protocol, wherein all consenting patients treated at MCC are sequenced. Genomic testing is funded by the ORIEN protocol.

For our on-study patients who are also co-enrolled in ORIEN (participant status is "Yes"), we will study patterns of tumor mutation burden and correlate genomic data to durability of treatment response and treatment resistance patterns using bioinformatics pipelines developed by the Biostatistics and Bioinformatics Shared Resource Facility at Markey.

12.1.5 The ORIEN Total Cancer Care is a very large clinical research protocol and data are stored within the Moffitt Data Warehouse (DW). For further details, please visit [www.oriencancer.org](http://www.oriencancer.org).

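### Section 11.2 names only Fisher's exact test for relating mutation data to outcomes, which suits neither censored times nor a continuous tumor mutation burden

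*Combined protocol and SAP*

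**What the plan says.** Section 11.2 (Data Analysis) covers the exome data in one short paragraph. Tailored processing and analysis pipelines will be applied, and then "exploratory comparisons of mutation data with response and clinical outcomes will be performed using" Fisher's exact test with FDR control. The paragraph does not mention TMB, a cut-point or a landmark time.

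For PFS the same section gives Kaplan-Meier estimates with confidence intervals. It adds: "Other time to event endpoints including OS will be estimated using the same methods". That is estimation only. No log-rank, Cox, rank or regression method is named for any genomic association.

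The questions are set elsewhere:

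- Secondary objective 1.2.3: "To evaluate potential biomarkers for durability of response, especially tumor mutation burden".
- Secondary objective 1.2.7: "To explore in a preliminary manner the response of genomic subsets to treatment focusing on tumor mutation burden", together with named gene mutations.
- Section 12.1.4, for patients co-enrolled in the sequencing protocol: "correlate genomic data to durability of treatment response and treatment resistance patterns using bioinformatics pipelines". No test is named there.

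Objective 1.3.2 repeats the TMB and mutation correlation among the exploratory items. Sequencing exists only for co-enrolled patients, so the number analysed is at most 36 and is not stated.

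**The concern.** The named test and the stated questions do not match. Fisher's exact test compares counts in categories. It suits a mutation that is present or absent against a response that is present or absent. PFS, OS and durability are times subject to censoring, and TMB is a number.

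To use Fisher's test on them, the analyst must choose a landmark and a TMB cut-point, and must decide what to do with patients censored before the landmark. If these choices are made after the data are seen, FDR control over the reported tests does not cover the alternatives that were tried. Cutting also discards information in a subset that has little to spare. At stake is how informative the biomarker results are. The estimate of efficacy is not at stake.

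**Working it through.** **The plan's own figure.** The only design calculation is in section 11.1: with 36 patients and 50% progression-free at 6 months, the one-sided 90% lower limit is 38%. The exact (Clopper-Pearson) limit for 18/36 is the 10th percentile of Beta(18, 19) = 0.382, so the figure reproduces. The plan states no power for the genomic comparisons, so the rest is simulation under assumptions.

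**Inputs from the documents.** Median PFS 6.3 months (the hypothesised value in the rationale for the combination, section 2.2.5); at most 36 patients; follow-up to 36 months (section 5.5).

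**Assumed inputs.** 18 or 36 patients sequenced; exponential times with proportional hazards; hazard ratio (HR) 0.7, 0.6 or 0.5 per SD of TMB; HR 0.5, 0.4 or 0.3 for a binary mutation at 50% prevalence; median OS 12 months; TMB split at its median; landmarks at 6 and 12 months for PFS and 12 months for OS. Two-sided 5%, before FDR control, 6,000 trials per cell.

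**Tests.**

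- Fisher: exact p-value on the 2x2 table of TMB half (or mutation) by event-free at the landmark.
- Cox score test: Z = U/√V, where U sums, over events, the patient's covariate minus its risk-set mean, and V sums the risk-set variances. With a binary covariate this is the log-rank test.
- Cox and log-rank were corrected to a true 5% level using null simulations. Fisher was run at nominal 5%, where its true level was 1.4-3.0%.
- Relative loss = 1 − (Fisher power / comparator power), computed before rounding.

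**Continuous TMB against PFS, landmark 6 months.**

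| n | HR per SD | Cox, continuous TMB | Log-rank, split TMB | Fisher | Loss vs Cox |
|---|---|---|---|---|---|
| 36 | 0.7 | 0.48 | 0.31 | 0.15 | 69% |
| 36 | 0.6 | 0.75 | 0.52 | 0.25 | 66% |
| 36 | 0.5 | 0.93 | 0.75 | 0.44 | 53% |
| 18 | 0.7 | 0.24 | 0.16 | 0.06 | 73% |
| 18 | 0.6 | 0.41 | 0.26 | 0.10 | 75% |
| 18 | 0.5 | 0.61 | 0.39 | 0.17 | 72% |

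Both cuts cost power. At n = 36 and HR 0.6, splitting TMB takes power from 0.75 to 0.52. Replacing times by a landmark table takes it to 0.25, partly because Fisher's test is conservative. Over all 18 TMB scenarios (both sizes, all three landmarks) the loss is 50-79%.

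**Other cases.**

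| Comparison | n | Loss with Fisher |
|---|---|---|
| Binary mutation, 6-month PFS or 12-month OS | 18 and 36 | 52-71% |
| Binary mutation, 12-month PFS | 18 | 52-56% |
| Binary mutation, 12-month PFS | 36 | 30-47% |
| TMB against binary response (vs rank-sum, nominal level) | 18 | 48-63% |
| TMB against binary response (vs rank-sum, nominal level) | 36 | 23-49% |

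**Checks.** For 35 events, HR 0.4 and equal groups, Schoenfeld's formula gives √(35/4) × |ln 0.4| − 1.96 = 2.71 − 1.96 = 0.75, so power is Φ(0.75) = 0.77. The simulated log-rank gave 0.73. A separate run used median PFS 6 months, HR 0.55 per SD and 10% lost by 6 months. At n = 18/24/36 Fisher had 17/21/35% and size-corrected Cox 50/61/80%, a loss of 1 − 17/50 = 66%, 1 − 21/61 = 66% and 1 − 35/80 = 56%.

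**A stricter threshold.** With HR 0.55 per SD and p < 0.005, an assumed stand-in for FDR control over about ten tests, Cox itself has only about 16/27/50% at n = 18/24/36.

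**The case against.** The strongest reply is that nothing rests on these comparisons. Section 11.2 calls them exploratory, 1.2.7 calls the genomic work preliminary, and 1.3.2 lists the TMB correlation as exploratory. No hypothesis is powered and no decision follows. This stands and sets the severity. It does not remove the point: 1.2.3 is a secondary objective without that qualifier, and exploratory work in few patients still benefits from a suitable test.

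A second reply is that the plan does not prescribe Fisher's test for TMB. Section 11.2 does not mention TMB, and both 11.2 and 12.1.4 refer to pipelines that could contain other methods. Durability is not defined in 1.2 or 11.2 and might be read as response at a fixed week, a yes/no outcome. This stands in part. A reader might infer that the plan forces every clinical outcome and TMB into 2x2 tables, but the text does not go that far. It does name one test for response and clinical outcomes, a phrase that naturally includes PFS and OS, and it offers no alternative.

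A third reply is that sample size is the main limit. This is also fair: under a stricter threshold or a weaker effect, Cox often misses the effect too. The ranking of the methods is unchanged.

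**Conclusion.** The mismatch is real and follows from the text alone. Applied to PFS, OS or durability, the only named test needs a landmark and, for TMB, a cut-point. Neither is stated, and patients censored before the landmark are left unclassified.

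The size is conditional. For continuous TMB against PFS or OS the power loss was 50-79% in every scenario run. A reader might infer that half the power is lost for all outcomes. That is not supported: at n = 36 the loss was 23-49% for TMB against binary response and 30-47% for a binary mutation against 12-month PFS. All figures rest on assumed effects and subset sizes, precede FDR control, and come from proportional-hazards data that favour Cox.

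A reader might also infer that excluding censored patients biases the comparison. The plan states no handling rule, so this is a possibility only.

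Severity is low: a cheap improvement to an exploratory analysis, with no effect on the primary endpoint.

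**What to change.** In section 11.2, replace the single named test with a short list:

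- Binary mutation against binary response: keep Fisher's exact test.
- Binary mutation against PFS, OS and duration of response: log-rank or Cox, with permutation p-values because the subset is small.
- TMB: analyse as continuous, using Cox (permutation p-values) for time-to-event outcomes and the Wilcoxon rank-sum test for response.
- Keep FDR control across the whole set, and keep the exploratory label.

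Say what durability of response means. If a landmark table or TMB split is also shown, fix the landmark, the cut-point and the handling of earlier censoring in advance.

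The cost is a few sentences and minor extra programming for the permutation p-values. No new data are needed. The change will not make a small sequenced subset adequately powered, and the text should not suggest that it does.
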